9.2 Clinical Procedures and Safety Evaluations

9.2.1 Informed Consent

Patients hospitalized for COVID-19 with a prior history of CVD and/or at least one risk factor for CVD will be approached and informed of the possibility of study participation. The benefits and risks of participating in the study will be explained to the patient. The patient will be provided with an opportunity to read the detailed information about the study in an informed consent form (ICF) and ask any questions he/she may have. Prior to conducting any study-related procedures, the patient must provide consent to participate by signing the Institutional Review Board/Research Ethics Board (IRB/REB) approved ICF.

9.2.2 Demography

This includes age, sex and race.

9.2.3 Standard 12-lead Electrocardiogram (ECG)

A 12-lead ECG will be performed at baseline, at Days 3, 5, 7, 14, 21, and 28 5 hours post morning dose (time window 3.5 – 6 hours).

The effect of CBD (CardiolRx™) on cardiomyocyte ion channel function has not been reported to date. One study assessed the effect of a product with equal THC and CBD content (Sativex) on QTc (Sellers et al. 2013). No effect was found. In the Abstracts of the 2017 meeting of the American Epilepsy Society, Van Landingham et al. from GW Pharmaceuticals presented the PK data for single normal and large doses of their CBD and assessed the impact on QTc (VanLandingham et al. 2017). No impact was identified. Another study of the effects of CBD on QT interval in children and young adults with epilepsy syndromes is listed on Clinical Trials.gov but was not completed because the investigator has been on medical leave and recruitment was difficult. Cardiol has contracted to have half-maximal inhibitory concentration (IC 50) values recorded for sodium, potassium and calcium channels in a human cardiac cell line. Until those results are available, the FDA has requested that the QTc intervals on repeated ECG recordings at the times of peak blood levels of CBD and its major metabolites are assessed after the morning dose of study medication. The time to peak blood level for CBD and its two major metabolites (7-hydroxy CBD and 7-Carboxy CBD) has been reported to be at approximately 4 hours after the dose has been taken (Tayo et al. 2020; Taylor et al. 2018). In our Phase I study the maximum concentration occurred at 5 hours post dose; this interval is specified for this protocol.

As noted in section 6.3 of the IB, there is considerable potential for drug-drug interactions (DDIs) in the patient population under study. Of particular concern is the potential for CBD to inhibit the metabolism of a drug(s) that has the ability to prolong the QTc interval. Therefore, if the QTc does increase after the institution of the study drug, the Investigator should consider this possibility, identify the concomitant medication responsible for it and adjust the dose of the medication as appropriate.

Because of this concern, an electrocardiogram (ECG) will be recorded every other day for the first 7 days of drug dosing and on Days 14, 21 and 28; the recording should be done 5 hours after the morning dose of the study drug (time window 3.5 – 6 hours). The ECG will be assessed by the Investigator at the clinical site, the QT interval measured (the QTc calculated) and recorded in the case report form (CRF), with a copy of the ECG appended. The QT interval is measured from the beginning of the QRS complex to the end of the T wave and averaged over three cardiac cycles. The average QT interval should be corrected for heart rate variability using Bazett's formula ($QT_c = QT / \sqrt{RR}$) or Fridericia's formula ($QT_c = QT / RR^{1/3}$) to create the QTc interval. Each patient should have the QTc measured using the same method on all designated days in the study. If the QTc interval increases to 500 msec or more – or increases 60 msec or more from the baseline recording on any one measurement, this will be reported as an SAE and the study medication will be discontinued.

The QT interval can be obtained from the automated measurements of the ECG recorder, unless the data quality is poor. It is the corrected value that is to be recorded in the CRF.

After 100 patients have completed the Day 28 assessment (or terminated the study earlier), the QTc data will be analyzed (unblinded) by the DSMC. If an impact on the QTc interval by the study drug has been found, the DSMC will evaluate the appropriateness of continuing the trial.

The presence of a bundle branch block represents a particular challenge in properly measuring the QTc interval. Following international recommendations, QT interval should be measured in leads showing the longest QT interval, which is usually in right precordial leads. In presence of a BBB, these leads are strongest affected by conduction delay and therefore hamper adequate measurement. A new formula for evaluation of the QT interval in patients with left bundle branch block (LBBB) was introduced in 2014:

$$QT_{mean} = QT_{BBB} - 50\% QRS_{BBB} \text{ (Bogossian et al. 2014)}$$

This formula has proved to be a reliable tool in clinical practice for QTc interval evaluation in patients with LBBB, right bundle branch block (RBBB) or bifascicular block. (Bogossian et al. 2020; Erkacic et al. 2020)

If the QTc interval increases to 500 msec or more – or increases 60 msec or more from the baseline recording on any one measurement, this must be reported as an SAE and the study medication must be discontinued.

Other clinically relevant ECG changes also need to be reported as an AE or SAE.

9.2.4 LVEF assessment by Echocardiography

The patient's LVEF will be assessed at baseline and at Day 28.

Each study will include 2-D echo images obtained from the standard parasternal and apical windows, with care taken to ensure on-axis views from all acoustic windows. LVEF will be calculated by standard techniques. LV cavity dimensions in systole and diastole will be measured, as well as thickness of the interventricular septum and posterior wall according to current guidelines. LV mass and mass index normalized for body surface area will be calculated using standard formulae (Otterstad et al. 1997).

Biplane Simpson's method (Devereux et al. 1986) will be used for measurement of LV end-diastolic (LVEDV) and end-systolic (LVESV) volumes. Volume measurements obtained by this method have been shown to be both accurate and reproducible, with variation in the range of -5% to +5%. It is anticipated that the image quality will be adequate for accurate endocardial tracing in > 90% of patients.

LVEDV, LVESV, and LVEF will be calculated and averaged over 5 cardiac cycles, 10 cardiac cycles in patients with atrial fibrillation.

9.2.5 Medical History

Data will be collected from patients at baseline consisting of medical history, including previous cardiac investigations, previous cardiac history, and current medications.

9.2.6 Clinical assessment

A routine clinical assessment is required at baseline, at Days 7, 14, 21, 28, 45 and 60. Any abnormality must be recorded.

Any subsequent change and new finding must be documented at each scheduled clinic visit, and reported as an (S)AE, if applicable.

9.2.7 Vital signs, body height and weight

Vital signs including blood pressure and heart rate will be recorded at each clinic assessment/visit. A calibrated sphygmomanometer and a cuff size appropriate for the patient's arm circumference will be used. The patient must be sitting, and must have rested for at least 5 minutes. The diastolic blood pressure is to be read at the disappearance of sounds (Korotkoff phase 5). If the disappearance of sound is not detectable, phase IV should be used. Any clinically relevant change in blood pressure or HR must be reported as an AE or SAE.

Body height is to be measured at baseline. Body weight must be measured at baseline, at days 7, 14, 21, 28, 45 and 60. Body weight at baseline will be used for the calculation of the amount of study medication to be administered throughout the treatment period.

9.2.8 Ordinal Outcome Scale

The scores for the Ordinal Outcome Scale will be collected at each visit:

- 1) not hospitalized and no limitations of activities;
- 2) not hospitalized, with limitation of activities, home oxygen requirement, or both;
- 3) hospitalized, not requiring supplemental oxygen and no longer requiring ongoing medical care
- 4) hospitalized, not requiring supplemental oxygen but requiring ongoing medical care
- 5) hospitalized, requiring any supplemental oxygen;
- 6) hospitalized, requiring noninvasive ventilation or use of high-flow oxygen devices;
- 7) hospitalized, receiving invasive mechanical ventilation or extracorporeal membrane oxygenation (ECMO);
- 8) MI or stroke diagnosed since randomization
- 9) death.

9.2.9 Suicide Severity Rating Scale (C-SSRS)

The C-SSRS is a questionnaire designed for the assessment of suicidal ideation and behavior in adolescents and adults.

To monitor for the emergence of suicidal ideation and behavior, subjects will undergo C-SSRS evaluations at baseline and at Day 28.

The questionnaire must be administered by an investigator or other individual that is suitably qualified by education or training. See Appendix 17.4 for a sample C-SSRS – Baseline/Screening version assessment and Appendix 17.5 for a sample 28-day post-dose C-SSRS assessment.

If there is a positive result for suicidality on the C-SSRS after screening (defined by a subject answering 'yes' to questions 4 or 5 on the suicidal ideation portion of the C-SSRS), the subject will be evaluated by an investigator or medically qualified sub-investigator for continuation in the study.

If a subject becomes suicidal during the study, an investigator or medically qualified sub-investigator should provide the appropriate treatment to the subject.

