8 INVESTIGATIONAL PRODUCTS, DOSE AND DURATION OF TREATMENT

8.1 *Investigational Product*

CardiolRx™ is pharmaceutically produced. It contains cannabidiol in a concentration of 100 mg/ml and is free of tetrahydrocannabinol (THC; <5 ppm).

8.2 *Administration, Dosage and Duration of Treatment*

Study drug will be administered orally (via syringe)* with food according to the following treatment schedule:

Study Day	a.m. dose [mg/kg of body weight]	p.m. dose [mg/kg of body weight]
	CardiolRx™ or placebo	CardiolRx™ or placebo
1	N/A	2.5
2	2.5	2.5
3	2.5	5
4	5	5
5	5	7.5
6 - 28	7.5	7.5

At each study visit, drug accountability will be done. New bottles of study medication will be dispensed at each study visit (Days 3, 5, 7, 14 and 21).

If the next higher dose is not tolerated, the patient should return to the last tolerated dose. The highest tolerated dose will be administered until Day 28 (4 weeks post randomization).

The maximum treatment period will be 28 days.

* If the patient requires mechanical ventilation, the study medication is administered through a naso-gastric tube.

Justification for Dosing Regimen

COVID-19 is an acute illness with, at times, rapid progression of symptoms and signs. Because of this, it seems important to increase the blood level of the investigational agent as quickly as possible to achieve the potential anti-inflammatory and anti-cytokine actions that are likely to be important in this population. However, this agent has not been administered previously to this population, so care must be taken to observe closely for

adverse drug effects or drug-drug interactions that might have significant negative consequences. A similar product containing a highly purified botanical extract of CBD has been approved for use in pediatric epilepsy to a dose up to 10 mg/kg twice daily (Devinsky et al. 2016). We have chosen to restrict the maximum dose in this COVID-19 population to 7.5 mg/kg b.i.d. because of the expected elderly and perhaps frail condition of some of the enrolled patients. Investigators are encouraged to decrease the dose if there are indications of intolerance of a given dose to the previously tolerated dose.

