- Study drug dose adjustment to 7.5 mg/kg b.i.d., if 5.0 mg/kg b.i.d. is well-tolerated (If 5.0 mg/kg b.i.d. is not tolerated, then dose decrease back to 2.5 mg/kg b.i.d.)
- Study drug accountability
- Retention of frozen samples for hs-troponin, NT-proBNP, d-dimer, hs-CRP, ferritin, TNF-alpha, IL-1 beta, IL-6, IL-10 and additional parameters of interest
- Retention of frozen samples for CBD levels

Day 7

- Clinical assessment
- Vital signs, including HR, blood pressure and weight
- 12-lead ECG, including QTc interval assessment 5 hours post morning dose (time window 3.5 – 6 hours)
- Assessment of Ordinal Outcome Scale
- AE and SAE recording
- Recording of changes in concomitant medications
- Study drug dose adjustment and accountability
- Local laboratory assessments, including CBC, AST/ALT, alkaline phosphatase, bilirubin, creatinine/eGFR, INR, lymphocyte count and LDH
- Retention of frozen samples for hs-troponin, NT-proBNP, D-dimer, hs-CRP, ferritin, TNF-alpha, IL-1 beta, IL-6, IL-10 and additional parameters of interest
- Retention of frozen samples for CBD levels

If the patient is discharged before Day 7, the assessments up to Day 7 will be carried out as out-patient or home visits. After Day 7, all remaining scheduled assessments will be carried out during out-patient visits.

Time windows for out-patient visits or home visits up to Day 7 are +/- 1 day; after Day 7, time windows are +/- 2 days.

Day 14

- Clinical assessment
- Vital signs, including HR, blood pressure and weight
- 12-lead ECG, including QTc interval assessment 5 hours post morning dose (time window 3.5 – 6 hours)
- Assessment of Ordinal Outcome Scale

- AE and SAE recording
- Recording of changes in concomitant medications
- Study drug dose adjustment and accountability
- Local laboratory assessments, including CBC, AST/ALT, alkaline phosphatase, bilirubin, creatinine/eGFR, INR, lymphocyte count and LDH

Day 21

- Clinical assessment
- Vital signs, including HR, blood pressure and weight
- 12-lead ECG, including QTc interval assessment 5 hours post morning dose (time window 3.5 – 6 hours)
- Assessment of Ordinal Outcome Scale
- AE and SAE recording
- Recording of changes in concomitant medications
- Study drug dose adjustment and accountability

Day 28

- Clinical assessment
- Vital signs, including HR, blood pressure and weight
- Chest X-ray
- 12-lead ECG, including QTc interval assessment 5 hours post morning dose (time window 3.5 – 6 hours)
- LVEF by echocardiography

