This scale is intended to be used by individuals who have received training in its administration. The questions contained in the Columbia-Suicide Severity Rating Scale are suggested probes. Ultimately, the determination of the presence of suicidal ideation or behavior depends on the judgment of the individual administering the scale.

Definitions of behavioral suicidal events in this scale are based on those used in The Columbia Suicide History Form, developed by [name] and [name], Conte Center for the Neuroscience of Mental Disorders (CCNMD), New York State Psychiatric Institute, [name]. (Oquendo M. A., Halberstam B. & Mann J. J., Risk factors for suicidal behavior: utility and limitations of research instruments. In M.B. First [Ed.] Standardized Evaluation in Clinical Practice, pp. 103 -130, 2003.)

For reprints of the C-SSRS contact [name]., New York State Psychiatric Institute, [name]; inquiries and training requirements contact [contact]

© 2008 The Research Foundation for Mental Hygiene, Inc.

PART 1 OF 5

SUICIDAL IDEATION	

Ask questions 1 and 2. If both are negative, proceed to "Suicidal Behavior" section. If the answer to question 2 is "yes", ask questions 3, 4 and 5. If the answer to question 1 and/or 2 is "yes", complete "Intensity of Ideation" section below.
	

1. Wish to be Dead Subject endorses thoughts about a wish to be dead or not alive anymore, or wish to fall asleep and not wake up. Have you wished you were dead or wished you could go to sleep and not wake up? If yes, describe:
	

2. Non-Specific Active Suicidal Thoughts General non-specific thoughts of wanting to end one's life/commit suicide (e.g., "I've thought about killing myself") without thoughts of ways to kill oneself/associated methods, intent, or plan during the assessment period. Have you actually had any thoughts of killing yourself? If yes, describe:
	

 Section below not applicable
	

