Actual Attempt: A potentially self-injurious act committed with at least some wish to die, as a result of act. Behavior was in part thought of as method to kill oneself. Intent does not have to be 100%. If there is any intent/desire to die associated with the act, then it can be considered an actual suicide attempt. There does not have to be any injury or harm , just the potential for injury or harm. If person pulls trigger while gun is in mouth but gun is broken so no injury results, this is considered an attempt. Inferring Intent: Even if an individual denies intent/wish to die, it may be inferred clinically from the behavior or circumstances. For example, a highly lethal act that is clearly not an accident so no other intent but suicide can be inferred (e.g., gunshot to head, jumping from window of a high floor/story). Also, if someone denies intent to die, but they thought that what they did could be lethal, intent may be inferred.	Yes  No 
Have you made a suicide attempt? Have you done anything to harm yourself? Have you done anything dangerous where you could have died? What did you do? Did you _____ as a way to end your life? Did you want to die (even a little) when you _____? Were you trying to end your life when you _____? Or Did you think it was possible you could have died from _____? Or did you do it purely for other reasons / without ANY intention of killing yourself (like to relieve stress, feel better, get sympathy, or get something else to happen)? (Self-Injurious Behavior without suicidal intent) If yes, describe:	Total # of Attempts <hr/>
Has subject engaged in Non-Suicidal Self-Injurious Behavior?	Yes  No 

PART 4 OF 5

 Section below not applicable	

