Interrupted Attempt: When the person is interrupted (by an outside circumstance) from starting the potentially self-injurious act (if not for that, actual attempt would have occurred). Overdose: Person has pills in hand but is stopped from ingesting. Once they ingest any pills, this becomes an attempt rather than an interrupted attempt. Shooting: Person has gun pointed toward self, gun is taken away by someone else, or is somehow prevented from pulling trigger. Once they pull the trigger, even if the gun fails to fire, it is an attempt. Jumping: Person is poised to jump, is grabbed and taken down from ledge. Hanging: Person has noose around neck but has not yet started to hang - is stopped from doing so. Has there been a time when you started to do something to end your life but someone or something stopped you before you actually did anything? If yes, describe:	Yes  No  Total # of interrupted _____
Aborted Attempt: When person begins to take steps toward making a suicide attempt, but stops themselves before they actually have engaged in any self-destructive behavior. Examples are similar to interrupted attempts, except that the individual stops him/herself, instead of being stopped by something else. Has there been a time when you started to do something to try to end your life but you stopped yourself before you actually did anything? If yes, describe:	Yes  No  Total # of aborted _____
Preparatory Acts or Behavior: Acts or preparation towards imminently making a suicide attempt. This can include anything beyond a verbalization or thought, such as assembling a specific method (e.g., buying pills, purchasing a gun) or preparing for one's death by suicide (e.g., giving things away, writing a suicide note). Have you taken any steps towards making a suicide attempt or preparing to kill yourself (such as collecting pills, getting a gun, giving valuables away or writing a suicide note)? If yes, describe:	Yes  No 

Following must be answered

Suicidal Behavior: Suicidal behavior was present during the assessment period?	Yes  No 
Suicide:	Yes  No 

PART 5 OF 5

 Section below not applicable	
Answer for Actual Attempts Only	

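### The C-SSRS rule that calls for investigator evaluation after screening reads only ideation questions 4 and 5, so a reported suicide attempt does not trigger it

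*Protocol*

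**What the plan says.** Protocol section 9.2.9 states the purpose and the schedule together: "To monitor for the emergence of suicidal ideation and behavior, subjects will undergo C-SSRS evaluations at baseline and at Day 28". A positive result after screening is then defined in a parenthesis as a yes to "questions 4 or 5 on the suicidal ideation portion of the C-SSRS". A positive patient must be evaluated by an investigator, or a medically qualified sub-investigator, for continuation in the study. A further sentence says that these same clinicians should give appropriate treatment to a patient who becomes suicidal. It does not define that state or refer to the scale.

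The Day 28 form is the Since Last Visit version in Appendix 17.5. On questions 1 and 2 it instructs: "If both are negative, proceed to 'Suicidal Behavior' section". On the rest of the ideation section it says: "If the answer to question 2 is 'yes', ask questions 3, 4 and 5". The behavior section follows. It begins with actual attempts ("Have you made a suicide attempt"), continues with interrupted attempts, aborted attempts and preparatory acts, and ends with a mandatory yes/no summary item, "Suicidal behavior was present during the assessment period".

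SAP section 9.3.2 tabulates ideation and behavior and gives shift tables from baseline to Day 28. It sets no clinical trigger.

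**The concern.** The definition of positive is closed. It names two ideation questions, offers them as the whole definition rather than as examples, and includes no behavior item. The scale is meant to detect behavior and the form records it, but the step that turns a form result into a clinical action ignores it. The ordering is also odd: a patient who reports intent without acting is sent for evaluation, while a patient who reports an attempt need not be.

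What is at stake is the safety handling of individual patients at and after Day 28. No efficacy estimate, error rate or sample size depends on it.

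**Working it through.** The plan gives no figure to reproduce. The check applies the rule in 9.2.9 to the answer patterns that the form allows.

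**Step 1. Answer patterns**

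| Question 1 | Question 2 | Questions 4 and 5 | Any behavior reported | Positive under 9.2.9 | Positive if the summary item is added |
|---|---|---|---|---|---|
| no | no | not asked | yes | no | yes |
| yes | no | not asked | yes | no | yes |
| either | yes | both no | yes | no | yes |
| either | yes | at least one yes | no | yes | yes |
| either | yes | at least one yes | yes | yes | yes |

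The first three rows are the gap. In the first two, the form's own skip instruction means that the questions defining a positive result are never put to the patient.

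**Step 2. Coverage of the rule**

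- Ideation questions read: 2 of 5.
- Behavior categories read: 0 of 4 (actual attempt, interrupted attempt, aborted attempt, preparatory acts). The form's separate item for completed suicide is not counted.

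**Step 3. What is left to decide when the form is completed**

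Inputs: the only scheduled C-SSRS after screening is at Day 28 (9.2.9 and Appendix 17.2.1). On dosing, section 8.2 says "The maximum treatment period will be 28 days". On visit timing, section 9.1 says "after Day 7, time windows are +/- 2 days". The remaining scheduled visits are Day 45 and Day 60.

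- Form completed between Day 28 − 2 = 26 and Day 28 + 2 = 30.
- Dosing remaining: at most 28 − 26 = 2 days.
- Follow-up remaining to nominal Day 60: 60 − 30 = 30 to 60 − 26 = 34 days.
- With the window applied to Day 60 as well: 58 − 30 = 28 to 62 − 26 = 36 days.
- Scheduled visits remaining: 2.

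**Step 4. Patients affected**

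The documents give no rate of suicidal behavior, so 0.1% to 1% is assumed. With the planned 422 patients:

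- 422 × 0.001 = 0.4
- 422 × 0.01 = 4.2

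Within the assumed range these are upper bounds. Some patients reporting behavior would also say yes to question 4 or 5 and so be positive already. Not every randomized patient would reach a Day 28 form, and the SAP introduction says that the study was terminated early.

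**The case against.** The strongest reply is that the evaluation has little left to decide and that other provisions cover the patient.

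- Dosing is over or nearly over at Day 28, and section 6.7.1 keeps patients who stop treatment in follow-up unless they withdraw consent.
- An attempt disclosed on the form would ordinarily be recorded as an adverse event at the same visit (9.1). If serious, it is assessed for causality by the clinician who examines the patient, and all adverse events are followed until resolved or stable (9.2.14.1).
- Clinical assessments are required at Days 28, 45 and 60 (9.2.6).
- The treatment sentence in 9.2.9 covers an attempt on any ordinary reading, and treating a patient implies evaluating that patient.

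Much of this stands, and it is why the point is minor. It does not remove the gap. None of these provisions links a behavior answer on the scale to the evaluation that 9.2.9 requires. The treatment sentence leaves its condition undefined and says only what should be done. Two features of the protocol also make an explicit rule useful. Section 9.2.14.1 tells sites not to ask patients about specific adverse events, which leaves the C-SSRS as the only scheduled structured question about attempts. Section 9.2.9 also lets a suitably qualified person other than an investigator administer the form, so the person who hears of an attempt may not be the one who must act on it.

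It is also fair to say that the assumed rate has no source in the documents. The finding rests on the wording, not on that rate.

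**Conclusion.** The concern holds. As written, section 9.2.9 classes a patient who reports an attempt, but does not answer yes to question 4 or 5, as not positive, and so does not require the evaluation. This is a faulty rule rather than missing detail, because the definition is complete and gives the wrong answer for that patient.

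Severity is minor. The effect is confined to safety handling over roughly the last month of follow-up, general reporting provisions lessen it, and the SAP summaries are untouched. The conclusion on the rule follows from the text alone. Only the count of patients depends on the assumed rate.

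**What to change.** In section 9.2.9, define a positive result after screening as a yes to ideation question 4 or 5, or a yes to the form's summary item on suicidal behavior. Keep the ideation threshold where it is, and leave the decision about a positive patient with the investigator. SAP section 9.3.2 needs no change.

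The cost is one clause, using an item that the form already makes mandatory. It does have to go through a protocol amendment (14.4.2) approved by the Steering Committee (12.4), so it is best bundled with other changes. The added workload is no more than the assumed 0.4 to 4.2 evaluations. Because the study ended early, the practical value now is in correcting the text before it is reused in another protocol.
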